Study protocol

Diaphragmatic and sternocleidomastoid muscle recruitment at various inspiratory loads with and without breathing instruction in healthy adults

Objectives

- (1) to investigate the relationship between sternocleidomastoid muscle recruitment and diaphragm thickness fraction during increasing inspiratory resistance in healthy adults.
- (2) to compare diaphragmatic and sternocleidomastoid muscle recruitment patterns with and without a standard diaphragmatic breathing instruction with increasing inspiratory resistance in healthy adults.

Method

Ethical committee approval

Ethical committee approval was granted by the Research Ethics Committee of Hong Kong Metropolitan University (ethics approval number: HE-OT2023/13).

Sample size calculation

Sample size will be determined by repeated-measures analysis of variance (ANOVA) using G*Power 3.1. Considering an effect size of 0.3, an alpha error probability of 0.05, a power of 0.80, the estimated sample size is 30 participants. An additional 20% of the cohort will be recruited to compensate for the predicted sample size attrition. The final estimated sample size will be at least 36 participants.

Participants

Participants ≥ 18 years of age with normal health will be recruited and screened for any of the following ‘exclusion’ criteria: (1) participants with known cardiovascular, pulmonary, musculoskeletal or psychiatric disorders; (2) pregnancy; (3) with respiratory symptoms (from flu or other respiratory infection during the 2 weeks prior to measurements).

Procedure

Upon arrival at the laboratory, eligible participants will first perform a standard spirometry lung function test. The maximum inspiratory pressure (MIP) will be determined with a pressure

threshold inspiratory loading device (POWERbreathe, K₂). Each participant will then be instructed to use the device to perform, in random order, 10 breaths at an inspiratory intensity of 30%, 40%, 50%, 60%, 70%, and 80% MIP. A rest period of 15 minutes will be allowed between each inspiratory pressure set of 10 breaths. Simultaneous surface electromyographic (sEMG) recording of the right sternocleidomastoid muscle and ultrasound of right diaphragmatic thickness will be conducted during each breath.

The entire recording procedure will be repeated on a separate day. During the repeat measurements, participants will be provided with specific breathing instruction to focus on the use of the diaphragm and to inhale air to the lower part of the chest. Practice trials will be conducted to ensure participant's understanding of diaphragmatic breathing.

Measurements

Spirometry respiratory function

Forced vital capacity, forced expiratory volume in 1 second, and MIP will be measured following the American Thoracic Society guideline protocol.

Diaphragmatic contraction

During each of the 60 breaths, thickness of the right diaphragm at the end of each tidal expiration and at the end of each forced inspiration will be measured using diaphragmatic ultrasonography (Mindray M9, Shenzhen, China). The recorded thickness over each set of 10 breaths will be averaged. The strength of diaphragmatic contraction will be reflected by the diaphragmatic thickening fraction (DTf), which is calculated as a ratio of [the difference between mean diaphragmatic thickness at the end of each inspiratory pressure and mean diaphragmatic thickness at the end of tidal expiration / the diaphragmatic thickness at the end of tidal expiration] x100%.

Recruitment of the sternocleidomastoid muscle

A Noraxon Ultium wireless sEMG system (Noraxon USA, Inc., Scottsdale, AZ, USA) will be used to detect the muscle recruitment activity of the right sternocleidomastoid muscle. On the 2 days of data collection, sEMG data over each set of 10 breaths will be averaged for data analysis.

Self-perceived exertion level

Self-perceived exertion level at the end of each 10-breath set at each inspiratory pressure, will be also recorded using the Borg's scale of Rate of Perceived Exertion.

Statistical analysis

All data will be analyzed using the IBM SPSS Statistics for Windows, Version 25.0 (Armonk, NY: IBM Corp).

Changes in DTf, muscle activity of sternocleidomastoid and fatigue during each inspiratory protocol will be analyzed using repeated-measures ANOVA.

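### Objective 1 asks how sternocleidomastoid recruitment relates to DTf, but the only planned analysis does not estimate or test that relationship

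*Combined protocol and SAP*

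**What the plan says.** The Objectives section sets two aims. The first is "to investigate the relationship between sternocleidomastoid muscle recruitment and diaphragm thickness fraction during increasing inspiratory resistance in healthy adults". The second compares recruitment patterns "with and without a standard diaphragmatic breathing instruction with increasing inspiratory resistance in healthy adults".

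The Statistical analysis section has two sentences. One names the software: "All data will be analyzed using the IBM SPSS Statistics for Windows, Version 25.0". The other is the whole analysis plan: "Changes in DTf, muscle activity of sternocleidomastoid and fatigue during each inspiratory protocol will be analyzed using repeated-measures ANOVA". The Sample size calculation section relies on the same method: "Sample size will be determined by repeated-measures analysis of variance (ANOVA) using G*Power 3.1".

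The data needed for Objective 1 will be collected. Under Procedure: "Simultaneous surface electromyographic (sEMG) recording of the right sternocleidomastoid muscle and ultrasound of right diaphragmatic thickness will be conducted during each breath". Both signals are reduced to one value per load. For the diaphragm, "The recorded thickness over each set of 10 breaths will be averaged". For the sternocleidomastoid, "sEMG data over each set of 10 breaths will be averaged for data analysis".

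**The concern.** A relationship between two measures is a property of their joint distribution. Repeated-measures ANOVA of one measure over load tests whether that measure's mean differs between loads. Setting two such results side by side shows whether the group means rise together, and nothing more. No correlation, regression, mixed model or other analysis linking the two measures appears anywhere in the protocol.

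If the plan is followed as written, one of its two objectives ends without an estimate, an interval or a test. If the investigators then add an analysis, they choose it after seeing the data. The choice matters because the objective has two readings: how far the two measures change together as load rises (load left out of the model), or how far they are coupled beyond their common response to load (load in the model). These are different quantities, and the protocol chooses neither.

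**Working it through.** **Inputs from the protocol.** Six loads (30% to 80% MIP), two days, one mean per 10-breath set, effect size 0.3, alpha 0.05, power 0.80, 30 participants raised to 36.

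**Assumed inputs, because the protocol gives none.** The same linear load trend in both measures unless stated; f = SD of the load means / error SD (the protocol's 0.3 has no named metric); intraclass correlation (ICC) 0.6. *Coupling* means the correlation between the two measures' errors in the same person at the same load. There were 10,000 simulated data sets per setting, and 6,000 per step for the detectable r.

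**1. The plan's own figure.** 30 × 1.2 = 36 reproduces the final sample size. The 30 cannot be uniquely reproduced, because the number of measurements, their correlation ρ and the sphericity factor ε are not stated. With f = 0.3, m = 6 and one group, noncentrality f²·N·m·ε/(1 − ρ) gives N = 14 (ρ = 0.5, ε = 1), 25 (ρ = 0, ε = 1) or 31 (ρ = 0, ε = 0.75). The alternative f²·(N − 1)·(m − 1)·ε with ε = 1 also gives 31. So 30 is attainable and is not in dispute here. It was sized for a change in means, not for an association.

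**2. ANOVA ignores the pairing.** For each measure, F = MS(load) / MS(load × person), and both terms come from that measure alone. Giving one person's sEMG series to another person's DTf series therefore changes neither F. As an illustration, one simulated data set was paired with person means in the same rank order and then in reverse order. Both F values stayed at 41.49 and 45.52, while the between-person correlation went from 0.94 to −0.95. Over repeated data sets (n = 30, f = 0.3):

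| True coupling | Mean F | ANOVA rejects | Mean r, load in model | Mean r, load left out |
|---|---|---|---|---|
| −0.6 | 4.29 | 0.880 | −0.599 | −0.444 |
| 0 | 4.30 | 0.887 | 0.000 | 0.097 |
| 0.6 | 4.28 | 0.878 | 0.600 | 0.639 |

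**3. The two readings differ.** Take a load score with SD 1 over six loads. The expected within-person sum of squares is then 6f² from the trend and 5 from error, so with zero coupling the within-person r without load is about 6f²/(5 + 6f²). At f = 0.3 this is 0.54/5.54 = 0.097; at f = 0.5 it is 1.5/6.5 = 0.231. Simulation, n = 30, zero coupling:

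| f | Mean r without load | Test without load rejects | Test with load rejects |
|---|---|---|---|
| 0 | 0.000 | 0.051 | 0.053 |
| 0.2 | 0.046 | 0.089 | 0.050 |
| 0.3 | 0.098 | 0.224 | 0.051 |
| 0.4 | 0.161 | 0.513 | 0.047 |
| 0.5 | 0.231 | 0.835 | 0.048 |

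With 36 people, the test without load rejects 0.256 at f = 0.3 and 0.892 at f = 0.5. With opposite trends at f = 0.3, mean r is −0.097 (rejection 0.216). If only one measure responds to load, mean r is −0.001 (0.049).

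**4. Precision available for an association.** Repeated-measures correlation has 30 × 5 − 1 = 149 df, or 144 with load as a six-level factor. By Fisher z with SE = 1/√(df − 1), an observed r of 0.30 at 144 df has a 95% CI of 0.145 to 0.441. These are best-case figures, because they require everyone to share one load slope. If person slopes vary independently in the two measures with SD s (in error SDs), a true residual r of 0.30 is estimated at about 0.30 × 5/(5 + 6s²):

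| s | Mean estimate (formula) | Unclustered test rejects, zero coupling | Clustered test rejects, zero coupling | True r detectable at 80% power, clustered: n = 30 / n = 36 |
|---|---|---|---|---|
| 0 | (0.300) | about 0.05 | – | 0.23 / 0.21 |
| 0.3 | 0.270 (0.271) | 0.053 | 0.059 | 0.26 / 0.24 |
| 0.5 | 0.231 (0.231) | 0.076 | 0.062 | 0.33 / 0.30 |
| 0.8 | 0.169 (0.170) | 0.137 | 0.067 | 0.56 / 0.51 |

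**5. The tempting shortcut.** A single Pearson correlation over all 30 × 6 = 180 points treats repeated values as independent. With no association at any level and no load trend, it rejects 0.102, 0.232 and 0.344 of the time at ICC 0.3, 0.6 and 0.8.

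**The case against.** The strongest reply is about meaning. Objective 1 speaks of rising resistance and the plan analyses changes, so the investigators may intend only a comparison of two load profiles, which ANOVA partly serves. The ANOVA sentence also lists three outcomes without saying they are modelled separately. Neither point closes the gap. A relationship between two measures ordinarily means association, and comparing patterns is closer to Objective 2. No joint model is named, and even an ANOVA crossing muscle with load would compare mean profiles rather than estimate association.

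Other points stand in part:

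- ICC, trend shape and slope variation are all assumed. At f = 0.3 as defined here, ANOVA power is about 88%, not the protocol's 80%, so the figures are illustrative and not calibrated to this trial.
- Rejections by the test without load are not false positives. When both measures follow load, that correlation is truly non-zero. The figures show that the two readings differ, not that one is wrong.
- The protocol does not propose a pooled Pearson correlation. That result is a warning about a likely later choice.
- No sEMG normalisation is stated, and raw amplitude may differ in gain between people. With log-normal gain of log-SD 0.5 or 1.0 (assumed), a true load-adjusted r of 0.30 averages 0.27 or 0.20, and clustered power falls from 95% to 87% or 65%. The remedy must therefore fix the scale too.
- This is a small laboratory study and the paired data are collected regardless, so nothing is lost irreversibly. That limits the severity but does not remove the point.

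**Conclusion.** The concern holds and should be fixed before analysis. The protocol names a method, and that method cannot answer one of its two objectives. This conclusion rests on comparing the Objectives with the Statistical analysis section and on the algebra of the F ratio; no assumed input is needed.

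The simulations show what hangs on a later choice. Under equal load trends and zero coupling, the two readings average 0.10 and 0.00 at f = 0.3, and 0.23 and 0.00 at f = 0.5. With 30 participants, the load-adjusted version can detect a true r of 0.23 at best, rising to 0.56 if load slopes vary between people with SD 0.8 of the error SD. All these figures depend on the assumptions listed.

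**What to change.** Add one paragraph to the Statistical analysis section that does the following:

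- Names one within-participant association analysis of the paired DTf and sEMG set means over the six loads: either a linear mixed model of DTf on person-mean-centred sEMG with participant effects, or repeated-measures correlation.
- Reports it without load (joint change with load) and with load as a categorical factor (coupling beyond the shared response), each with a 95% CI that allows for clustering by participant, by a robust standard error or a participant-level bootstrap. Choose one of these in advance.
- States which version answers Objective 1 and on which day's data. The uninstructed day is the natural choice, since only Objective 2 mentions instruction.
- States the sEMG scale, preferably one that can be computed from the recorded breaths and removes differences in gain between people.
- Rules out one Pearson correlation over all participant-by-load points, and notes that the load-adjusted estimate of residual coupling is attenuated if people differ in load slope.

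The cost is this wording plus 5 degrees of freedom for the load-adjusted version: 144 rather than 149 with 30 participants, 174 rather than 179 with 36. No new data or visits are needed, provided the sEMG scale comes from the recorded breaths.

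### Does the sample size of 30 depend on perfect sphericity across the six loads, and does the ANOVA need a named correction?

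*Combined protocol and SAP*

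**What the plan says.** The Sample size calculation section names the method and software, "Sample size will be determined by repeated-measures analysis of variance (ANOVA) using G*Power 3.1", and then gives the inputs and result: "Considering an effect size of 0.3, an alpha error probability of 0.05, a power of 0.80, the estimated sample size is 30 participants". A further 20% brings the target to at least 36. The section does not state the effect under test, the number of measurements, the correlation among them, the nonsphericity epsilon or G*Power's effect-size option.

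The design has two within-person factors. Each participant performs "10 breaths at an inspiratory intensity of 30%, 40%, 50%, 60%, 70%, and 80% MIP", in random order, and "The entire recording procedure will be repeated on a separate day", this time with breathing instruction. Objective (2) is to compare "recruitment patterns with and without a standard diaphragmatic breathing instruction with increasing inspiratory resistance in healthy adults".

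The only sentence on inference, in the Statistical analysis section, is: "Changes in DTf, muscle activity of sternocleidomastoid and fatigue during each inspiratory protocol will be analyzed using repeated-measures ANOVA". It names no sphericity test, correction or alternative model, and it does not list the factors or interactions.

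**The concern.** A load effect or an instruction-by-load interaction over six loads has 5 numerator degrees of freedom, and the ordinary repeated-measures F is exact for it only under sphericity (epsilon = 1). Readings at neighbouring loads are likely to be more alike than readings at distant loads. Randomising the order of the loads does not remove that, so epsilon below 1 is plausible.

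Two things would then be at stake.

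- **Type I error.** An uncorrected F rejects too often, however the 30 was obtained.
- **Power.** A corrected F holds the error rate, but if the 30 was computed at epsilon = 1 it has less than 80% power.

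The worry is sharpened because a simple six-load calculation, with no correlation entered and epsilon left at 1, lands on 30.

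**Working it through.** **Inputs.** From the Sample size calculation section: effect size 0.3, alpha 0.05, power 0.80, N = 30. From the Procedure section: six loads, one group, two days. Assumptions: 0.3 is Cohen's f (f² = 0.09); every correlation and epsilon below is assumed, because the documents give none.

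**Formulas.** For m repeated measurements, power comes from the noncentral F with df1 = (m − 1)ε and df2 = (N − 1)(m − 1)ε.

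- Option A (no correlation input): λ = ε f² N (m − 1)
- Option B (correlation ρ entered): λ = ε f² N m / (1 − ρ)

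**Step 1: reproduce 30.** Option A, m = 6, ε = 1: λ = 0.09 × 30 × 5 = 13.5 on 5 and 145 df, power 80.6%. N = 29 gives 79.0%, so N = 30. The attrition step also follows: 30 × 1.2 = 36.

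**Step 2: how tightly is 30 tied to ε = 1?** On option A, N stays at 30 at ε = 0.99 (80.3%) and ε = 0.985 (80.1%), and is 31 at 0.95. If N − 1 replaces N in λ, ε = 1 already needs 31 (79.0% at 30). So the match at perfect sphericity depends on the exact form of λ, and where it holds it does not need ε to be exactly 1.

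**Step 3: other routes to 30 (option B).**

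| Effect | ρ | ε | N |
|---|---|---|---|
| Two conditions (1 df) | 0.36 to 0.38 | not applicable | 30 |
| Six loads | 0 | 0.76 to 0.79 | 30 |
| Six loads | 0.3 | 0.46 to 0.47 | 30 |
| Six loads | 0.5 | 0.29 | 30 |

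The first row has no sphericity condition to violate. The other three already contain an allowance.

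**Step 4: power if the option A route was used.** Take equal variances and a correlation that falls by a factor of 0.5, 0.7 or 0.9 per load step.

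| Factor per step | ε | Power at 30 | N for 80% |
|---|---|---|---|
| (sphericity) | 1 | 80.6% | 30 |
| 0.5 | 0.77 | 72% | 36 |
| 0.7 | 0.63 | 65% | 41 |
| 0.9 | 0.50 | 58% | 48 |

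On option B with ρ = 0.5, the same 30 participants have 93.7% power at ε = 0.5. At one and the same epsilon, then, power could be 58% or 94%, and the documents do not favour either figure.

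**Step 5: type I error at n = 30, simulated under the same three patterns.**

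| Factor per step | Uncorrected F | Greenhouse-Geisser |
|---|---|---|
| 0.5 | 6.6% | 4.2% |
| 0.7 | 7.7% | 4.5% |
| 0.9 | 9.0% | 4.9% |

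The Box approximation, P(F(5ε, 145ε) > F0.95(5, 145)), gives 6.8%, 8.2% and 9.8%, and 14.2% at the lower bound ε = 1/5 = 0.2.

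**Step 6: the instruction main effect.** With two conditions it has 1 df and no sphericity condition. Thirty participants with both days give 80% power for a paired standardised difference of about 0.53.

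**The case for a change.** The best argument for acting is that the type I error result does not depend on how 30 was computed. Whenever epsilon is below 1, an uncorrected 5-df F is liberal. One sentence naming the correction would hold the error at or just under 5% and would remove a choice between p values after the data are seen. A second sentence would tell the reader which effect has 80% power.

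Much of this stands. Both omissions are real, nothing elsewhere in the document fills them, and a fuller protocol would have covered them.

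What does not follow is that the plan is wrong. The inflation needs two things the documents do not supply: a correlation pattern, and an analyst who reports the uncorrected line. The Statistical analysis section commits to neither a corrected nor an uncorrected F. The procedure in SPSS, the named package, prints the Greenhouse-Geisser and Huynh-Feldt tests alongside the uncorrected one, so using a corrected test needs no new analysis. On the sample size, the remedy would consist of blanks that only the sponsor can fill, and filling them might show that an allowance was already made. The section also leaves open which factors the ANOVA contains, so a sentence prescribing corrections for particular terms would presuppose a model that it does not state.

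**Conclusion.** No change to the plan follows. The stated 30 reproduces, as does the 36, and no stated power or sample size is shown to be wrong. That the 30 rests on perfect sphericity is one reconstruction among several. It assumes that 0.3 is Cohen's f, that the tested effect has 5 df, and that no correlation was entered; other equally admissible inputs reach 30 with an allowance for nonsphericity or with no need of one. The power figures of 72%, 65% and 58% are therefore illustrative.

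The possible type I error, about 6.5% to 9% instead of 5% under the assumed autoregressive patterns, arises only if the uncorrected test is the one reported. The 14% figure is the mathematical limit at epsilon 0.2, not an expected value. What remains is a gap in reporting detail in a small physiology study in healthy adults, which an analyst closes sensibly by reading the corrected line of the output. It costs no data and does not alter the design.

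### The uninstructed session always comes first and the instructed session second, so the average instruction contrast in Objective 2 also contains any second-session effect

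*Combined protocol and SAP*

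**What the plan says.** The second objective is "to compare diaphragmatic and sternocleidomastoid muscle recruitment patterns with and without a standard diaphragmatic breathing instruction" as inspiratory load rises (Objectives).

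The Procedure section sets out two sessions. In the first, "Each participant will then be instructed to use the device to perform, in random order, 10 breaths at an inspiratory intensity of" 30% to 80% of MIP in six steps. Then "The entire recording procedure will be repeated on a separate day", and "During the repeat measurements, participants will be provided with specific breathing instruction". The next sentence adds that "Practice trials will be conducted to ensure" that participants have grasped the technique. The randomisation applies to the loads. The Procedure describes no random or alternating order for the two sessions, no group that repeats the session uninstructed, and no familiarisation set before the first recording.

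The whole analysis statement is "Changes in DTf, muscle activity of sternocleidomastoid and fatigue during each inspiratory protocol will be analyzed using repeated-measures ANOVA" (Statistical analysis). It names no session term and no session-by-load interaction, and it sets no limit on how a difference between sessions may be interpreted.

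Under Sample size calculation, "the estimated sample size is 30 participants", and after a 20% allowance for attrition, "The final estimated sample size will be at least 36 participants".

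**The concern.** Instruction and session coincide in every participant. Someone arriving for the second session has already done 60 recorded loaded breaths (six loads of ten) on the device, and sEMG and ultrasound are recorded on two different days. Any change from learning, prior exposure or day-to-day measurement goes into the same contrast as the instruction.

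A difference in the session averages could therefore be taken for an effect of instruction when part or all of it belongs to the second session. A null average could likewise be two opposite effects cancelling. This touches one of the two stated objectives, and it cannot be repaired once the data are collected.

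**Working it through.** **The plan's own figure.** The inflation reproduces: 30 × 1.2 = 36. The 30 cannot be checked uniquely, because the number of measurements, their correlation and the effect-size convention are not stated. The point here does not depend on it.

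**Can session and instruction be separated?** Write the load-averaged outcome of one participant as

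Y = μ + σ·(second session) + ι·(instructed) + error.

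The only two kinds of record are:

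| Session | intercept | second session | instructed |
|---|---|---|---|
| Day 1 | 1 | 0 | 0 |
| Day 2 | 1 | 1 | 1 |

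The last two columns are identical, so the matrix has rank 2 for 3 parameters. The mean of day 2 minus day 1 estimates ι + σ, and only the sum. A larger sample makes the estimate of the sum more precise but does not split it. A counterbalanced order (assuming no carry-over) or a parallel group repeating the session uninstructed would each give rank 3.

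**What is not affected.** Comparisons between loads within one session hold the session fixed, and load order is randomised. The relationship in Objective 1, analysed within a session, does not use the day-2 minus day-1 contrast.

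**The load profile.** Let the day effect at load k be d(k). The session-by-load interaction compares the day difference at load k with that at load j, so d contributes d(k) − d(j).
- Constant additive shift, d(k) = c: the contribution is c − c = 0, and the interaction is protected.
- Proportional change in sEMG amplitude by a fraction g, with true amplitude A(k): d(k) = g·A(k), and the contribution is g·[A(k) − A(j)]. This is not zero wherever amplitude differs between loads. The Measurements section averages sEMG over each set and describes no normalisation, so such a change would enter the interaction.

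**Illustration of size for the average contrast.** Assumptions, none of them in the documents: the sessions are compared by the session main effect of a 2 × 6 within-subject ANOVA at two-sided 5% (equivalent to a paired t-test on load averages), the true instruction effect is zero, and the session shift is δ in units of the SD of the paired difference.

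Rejection probability = P[F′(1, n − 1; λ) > critical F], with λ = n·δ². Critical F is 4.18 for n = 30 and 4.12 for n = 36.

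| δ | λ (n = 30) | Rejects (n = 30) | λ (n = 36) | Rejects (n = 36) |
|---|---|---|---|---|
| 0 | 0 | 5.0% | 0 | 5.0% |
| 0.1 | 0.30 | 8.3% | 0.36 | 9.0% |
| 0.2 | 1.20 | 18.5% | 1.44 | 21.5% |
| 0.3 | 2.70 | 35.5% | 3.24 | 41.7% |

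The n = 36 column assumes no dropout. Since 36 exists to cover attrition from 30, n = 30 is the more relevant column.

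**The case against.** **Uninstructed-first may be deliberate.** A learned breathing technique may carry over into a later uninstructed session, so the fixed order is defensible. This stands, although the documents do not state it. It is a reason not to demand randomised order, but it does not remove the second-session effect from the average contrast.

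**The objective may concern only the load profile.** Recruitment patterns as load rises can fairly be read that way, and a constant day shift then drops out. This stands in part. The plan does not name the interaction that would carry this reading, and the protection fails for a day effect that varies with load.

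**No session effect is shown.** Correct. Nothing in the documents supports a particular shift, or any shift, and the rates above are for a test the plan does not name. A reader might infer that a false positive is likely or that the study is biased by a known amount. The documents do not support that. They support only that the two effects cannot be told apart.

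**Practice trials are part of giving the instruction.** Also correct. A reader might count them as a further confounder, but they serve participants' understanding of the technique and belong to the intervention being tested.

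**Participants are not new to the device on day 1.** MIP is determined with the same loading device before the loaded sets. This gives some exposure, but maximal efforts are not loaded sets of ten breaths. DTf is also a ratio to end-expiratory thickness, so a proportional day-to-day shift in measured thickness would cancel for that outcome. Neither feature covers learning or sEMG amplitude.

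**Conclusion.** The point holds for the average with-versus-without-instruction difference in Objective 2. As designed, that difference is the instruction, including its practice trials, plus any second-session effect. This follows from the Procedure section alone and needs no numerical assumption. The rejection rates (5% with no shift, 18.5% at 0.2 SD and 36% at 0.3 SD, n = 30) are illustrative and rest on assumed shifts and an assumed test.

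A reader might go further and conclude that Objective 2 cannot be answered at all, or that the session order must be changed. The documents do not support either. The load profile can still be compared, subject to the limit on load-varying day effects, and there is a plausible reason for the present order. The study can run as designed. What should change before it starts is the analysis specification and the claim the average contrast is allowed to carry.

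**What to change.** 1. In the Statistical analysis section, specify a session-by-load repeated-measures ANOVA for Objective 2, and add there and under the objective: *The contrast is the instructed second session versus the uninstructed first session. The average difference will not be attributed to instruction alone. The session-by-load interaction is free of a constant additive day shift, but not of a day effect that varies with load, including a proportional change in sEMG amplitude between days.* Cost: protocol wording only.

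2. In the Procedure section, add a short set of uninstructed familiarisation breaths on the loading device before day-1 recording, beyond the MIP test. This reduces the learning difference but does not remove it, since day 2 still follows 60 recorded breaths. Cost: a few minutes on day 1.

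Neither change affects sample size, session order or equipment. Randomising the session order, or adding a group that repeats the session uninstructed, is optional: the first risks carry-over of a learned technique, and the second lowers power at a given sample size.

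### No masking of the ultrasound measurement is described, and the instructed session always comes second, so a reading error that differs between days could pass for an instruction effect on DTf

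*Combined protocol and SAP*

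**What the plan says.** The protocol's Objectives make DTf central twice: objective 1 relates it to sternocleidomastoid recruitment as load rises, and objective 2 compares recruitment with and without instruction in the same people.

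- **Acquisition.** Under Procedure, "ultrasound of right diaphragmatic thickness will be conducted during each breath", alongside surface EMG. The six loads are taken in random order.
- **Measurement.** Under Measurements, Diaphragmatic contraction, right diaphragm thickness at end-expiration and end-inspiration "will be measured using diaphragmatic ultrasonography" for each of the 60 breaths. It is then averaged within each 10-breath set.
- **Condition.** Everything is repeated on another day, and on that day "participants will be provided with specific breathing instruction to focus on the use of the diaphragm", with practice trials. Nothing in the text randomises or counterbalances the order of the two conditions.

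The protocol does not say who operates the ultrasound, who takes the thickness values, whether images are stored for later reading, or whether anyone is masked to session or load.

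**The concern.** A thickness reading can be influenced by what the reader expects, and here the expected directions are plain: a thicker diaphragm at higher load, and a thicker one when the participant has been told to use it. Because the instructed condition is the second day for everyone, being present is enough to know the condition.

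The contrast in objective 2 is within person. A shift in reading that arises on one day and not the other cannot be told apart from the effect being sought. The EMG outcome is a recorded signal and would not share that error. A bias confined to DTf could therefore look like work moving towards the diaphragm, which is the recruitment pattern under study. A larger sample would not help, because the error is systematic.

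**Working it through.** **What the plan supplies.** It gives no thickness, no SD of DTf and no reading error, so there is no plan figure on this point to reproduce. Its sample size (30, raised to 30 x 1.2 = 36) enters only as a count and as n below.

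**Step 1. How a reading error enters DTf.** From the definition under Diaphragmatic contraction, with Ti the end-inspiratory and Te the end-expiratory thickness:

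DTf = 100 x (Ti - Te) / Te

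An error e in Ti alone shifts DTf by 100 x e / Te. With errors e1 and e2 on the two days and the same Te, the instruction contrast shifts by

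100 x (e2 - e1) / Te

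If e1 = e2 the shift is zero. Only the between-day difference matters for objective 2.

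**Step 2. Illustration.** Both inputs are assumptions: Te of 1.5 to 2.5 mm, and a between-day difference d = e2 - e1 of 0.05 or 0.1 mm.

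| d (mm) | Te = 1.5 mm | Te = 2.0 mm | Te = 2.5 mm |
|---|---|---|---|
| 0.05 | 3.3 points | 2.5 points | 2.0 points |
| 0.1 | 6.7 points | 5.0 points | 4.0 points |

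For example, 100 x 0.1 / 1.5 = 6.7 and 100 x 0.1 / 2.5 = 4.0. This takes the error to lie at end-inspiration only. Over-reading both phases equally leaves the numerator unchanged and enlarges the denominator, so DTf falls. Under-reading end-expiration adds to the upward shift.

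**Step 3. Averaging.** If each of the 10 readings in a set carries the same error e, their mean carries e. Only the random part shrinks.

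**Step 4. Effect on the test.** Take a two-sided paired t test at 0.05 as a simple stand-in for the instructed-versus-uninstructed contrast. Assume no true difference and a between-day bias of b SDs of the paired difference. The rejection rate comes from the noncentral t with n - 1 degrees of freedom and noncentrality b x sqrt(n); at n = 36 and b = 0.2 that is 0.2 x 6 = 1.2.

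| b (assumed) | n = 30 | n = 36 |
|---|---|---|
| 0 | 5.0% | 5.0% |
| 0.1 | 8.3% | 9.0% |
| 0.2 | 18.5% | 21.5% |
| 0.3 | 35.5% | 41.7% |
| 0.5 | 75.4% | 83.1% |

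Steps 2 and 4 cannot be joined, because without an SD of DTf a shift in points cannot be converted to b.

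**Step 5. Reading workload.** 36 participants x 2 days x 60 breaths x 2 phases = 8,640 readings. As clips, 36 x 2 x 6 loads = 432 sets, each with 10 x 2 = 20 readings, and 432 x 20 = 8,640. The plan needs these readings whichever way they are taken.

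**The case against.** A reader might infer that the operator is known to be unmasked to both load and instruction, that the load setting is in view, and that every reading is made with that knowledge. The documents do not support this. They name no operator or reader and do not say who sets or sees the load. The wording on measuring during each breath leans towards live reading but does not exclude taking thickness later from stored images. That part of the objection stands. What the text does establish is narrower: no masking is described, and the session alone reveals the condition to anyone measuring in it.

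The second objection is to the size. An error common to both days cancels in objective 2, and load expectation common to both days does not create an instruction effect. Both stand, which is why the illustration uses a between-day difference and load-related error is tied to objective 1 only. The error and thickness values are assumed, and there is no DTf variability to judge 4.0 to 6.7 points against. That also stands: the figures show sensitivity, not an expected bias.

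The third is that this is only missing detail. That does not hold. A team following the protocol as written would measure in session with nothing to stop expectation entering the readings, and a less exposed method is available at modest cost.

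**Conclusion.** The point holds in this form: in-session measurement with no masking described, and instruction always on the second day, leave DTf open to reading expectation. A between-day difference in reading error would bias objective 2, and an error that varies with load would bias objective 1.

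On the assumed inputs, 0.1 mm moves the DTf contrast by 4.0 to 6.7 points and 0.05 mm by 2.0 to 3.3 points. The true size, and whether any such error will occur, cannot be derived from the documents. It does not follow that an observed instruction effect would be an artefact of reading, and the point does not alter the sample size. It is worth correcting because the protection is inexpensive and must be arranged before scanning: images that are not saved cannot be re-read.

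**What to change.** State in the protocol who scans and who reads, and add the following:

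- Save the clip of every 10-breath set under a code that hides participant, day and load.
- Have the same operator measure all thicknesses offline, in random order, after both days are complete.
- Unmask only after the measurement file is locked.

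If masked offline reading is already intended, writing it down is enough.

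The cost is clip storage, file coding, offline reading time and the loss of immediate on-screen values. No extra reader, scan or participant is needed.

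Two limits should be acknowledged. Masked reading does not remove expectation at acquisition, such as probe placement. Nor does it touch the separate confounding of instruction with day order, which would remain under perfect masking.
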